### **7.3 Lost to Follow-up**

A participant will be considered lost to follow-up if he or she repeatedly fails to return for scheduled visits and no contact has been established by the time the study is completed (see Section [4.4](#)).

Participants who decline to continue participation in the study, including telephone contact, should be documented as “withdrawal of consent” rather than “lost to follow-up.”

Investigators should document attempts to re-establish contact with missing participants throughout the study period. If contact with a missing participant is re-established, the participant should not be considered lost to follow-up and evaluations should resume according to the protocol.

The following actions must be taken if a participant fails to return to the clinic for a required study visit:

- The site must attempt to contact the participant and reschedule the missed visit as soon as possible and counsel the participant on the importance of maintaining the assigned visit schedule and ascertain whether or not the participant wishes to and/or should continue in the study.
- Before a participant is deemed lost to follow-up, the investigator or designee must make every effort to regain contact with the participant (where possible, 3 telephone calls and, if necessary, a certified letter to the participant’s last known mailing address or local equivalent methods). These contact attempts should be documented in the participant’s medical record.
- Should the participant continue to be unreachable, he/she will be considered to have been lost to follow-up from the study.

Discontinuation of specific sites or of the study as a whole are handled as part of [Appendix A](#).

## **8 STUDY ASSESSMENTS AND PROCEDURES**

Study procedures and their timing are summarised in the SoA ([Table 1](#) and [Table 2](#)). Data collection following study analysis until the end of the study is described below.

- Protocol waivers or exemptions are not allowed.
- Immediate safety concerns should be discussed with AstraZeneca immediately upon occurrence or awareness to determine if the participant should continue or discontinue study intervention.

- Adherence to the study design requirements, including those specified in the SoA, is essential and required for study conduct.
- All screening evaluations must be completed and reviewed to confirm that potential participants meet all eligibility criteria. The investigator will maintain a screening log to record details of all participants screened and to confirm eligibility or record reasons for screening failure, as applicable.
- Procedures conducted as part of the participant's routine clinical management (eg, blood count) and obtained before signing of the ICF may be utilised for screening or baseline purposes provided the procedures met the protocol-specified criteria and were performed within the time frame defined in the SoA.

### **Data Collection Following Study Analysis until the End of the Study**

Following the DCO2 for the primary efficacy endpoint, participants will continue with all assessments as indicated in the SoA.

For SAE and AE reporting and laboratory assessment collection after final analysis, see Section [8.3.11](#).

After the final DCO and database closure, only SAEs will be reported for the purposes of this study (see Section [8.3.11](#)).

## **8.1 Efficacy Assessments**

### **8.1.1 Imaging of the Target PN**

In 2013, consensus recommendations for the imaging of PN were issued by an international working group (REiNS) who recommended MRI volumetric PN assessment as preferable to all other MRI analysis techniques. MRI with volumetric analysis is recommended to sensitively and reproducibly evaluate changes in PN size in clinical studies. Volumetric analysis requires adherence to specific imaging recommendations and a 20% volume change was chosen to indicate a decrease or increase in PN size ([Dombi et al 2013](#)).

Extent of PN in patients with NF1 can be very substantial, and may not allow for all PNs to be followed using volumetric MRI. Prior to starting treatment on this study, the investigator must select a single target PN. The target PN is defined as the clinically most relevant PN, which is measurable by volumetric MRI analysis. If there is a second PN that is also considered clinically relevant, the investigator may select this as a non-target PN; only one non-target PN can be selected. Non-target PNs must also be measurable. AstraZeneca's appointed imaging CRO will measure the target PN and non-target PN (if applicable). However, the management of participants will be based upon the results of the PN assessments conducted by the investigator using their standard of care methods.

The MRI Images, including unscheduled visit scans, will be collected on an ongoing basis and sent to an AstraZeneca-appointed imaging CRO for QC, storage, and for ICR. The details about target PN location (most clinically relevant PN) and non-target PN location (if relevant) will also be collected to provide to the independent reviewer. Digital copies of all original scans should be stored at the investigator site as source documents. An independent central review of images will be performed for the assessment of efficacy according to the REiNS criteria. In general, results of these independent reviews will not be communicated to investigators, and results of investigator PN assessments will not be shared with the central reviewers. However, if the investigator requests unblinding due to suspected progression during the randomised period, and the request is deemed appropriate, the relevant MRI scans will be assessed by ICR per REiNS criteria. Unblinding will only be permitted if the participant has progression on imaging as determined by ICR. If the participant was on placebo they will be allowed to crossover to selumetinib treatment.

Screening imaging evaluation:

- Identify and select the inoperable target PN (plus a maximum of one additional non-target PN). Should there be more than 2 inoperable PNs that meet the criteria for selection, the 2 most clinically relevant PNs will be followed by volumetric MRI analysis.
- Perform volumetric MRI evaluation on the selected index PNs as outlined in the MRI acquisition guidelines.

On study imaging evaluation:

Unless clinically indicated otherwise, and as defined in [Table 1](#), volumetric MRI of the target and non-target PNs should be performed at every 4 cycles ( $16 \pm 1$  weeks) relative to the date of first dose for the first 24 cycles. From the end of Cycle 24, tumour assessments will be performed every 6 cycles ( $24 \pm 1$  weeks), as long as the participant remains on study intervention. Volumetric MRI assessment of the target and non-target PNs according to the REiNS criteria will be performed by the central imaging vendor. If an unscheduled assessment is performed (eg, to investigate clinical signs/symptoms of progression) and the participant has not progressed, the subsequent assessments at the next scheduled visit must be performed.

The REiNS criteria as assessed by volumetric MRI of the target PN performed by the ICR are as follows:

- Complete response: disappearance of the target PN. The CR is considered unconfirmed at first detection and confirmed when observed again at a consecutive scan within 3 to 6 months.

- Partial response: decrease in the volume of the target PN by 20% or more compared to baseline. The PR is considered unconfirmed at the first detection and confirmed when observed again at a consecutive scan within 3 to 6 months.
- Stable disease: insufficient volume change to qualify for either PR or PD.
- Progressive disease: increase in the volume of the target PN by 20% or more compared to baseline or the time of best response after documenting a PR. The appearance of new PN (with the exception of new discrete subcutaneous neurofibromas as noted below) which is unequivocally and completely distinct and separate from the target PN and the non-target PN, or unequivocal progression of an existing non-target PN is also considered PD. In this study unequivocal progression is defined as an increase in the volume of the non-target PN by 20% or more compared to baseline.

The clinical appearance of new discrete subcutaneous neurofibromas does not qualify for disease progression.

Before submitting the MRI scans to the central review vendor site staff should ensure that the target PN and non-target PN (if applicable) are fully visible on the scans.

In the event that a participant taking part in the study had a target PN resection and remained in the study, MRI scans will continue to be collected.

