## **7 DISCONTINUATION OF STUDY INTERVENTION AND PARTICIPANT DISCONTINUATION/WITHDRAWAL**

### **7.1 Discontinuation of Study Intervention**

It may be necessary for a participant to permanently discontinue (definitive discontinuation) study intervention. If study intervention is permanently discontinued, the participant will remain in the study to be evaluated for 30 day safety follow-up. The investigator should instruct the participant to contact the site before or at the time if study intervention is stopped. A participant that decides to discontinue study intervention will always be asked about the reason(s) and the presence of any AEs. The reason for discontinuation should be documented in the source document and the appropriate section of the eCRF.

Participants who have permanently discontinued from further receipt of study intervention will need to be discontinued from the IRT. All study intervention should be returned by the participant at their next on-site study visit or unscheduled visit.

Participants may be discontinued from study intervention in the following situations:

- Investigator determination that the participant is no longer benefiting from study intervention.
- An AE that, in the opinion of the investigator or AstraZeneca, contraindicates further dosing.
- Any AE that meets criteria for discontinuation defined in the dose modification guidelines for management of study intervention-related toxicities (see Section 6.6).
- Participant decision. The participant is at any time free to discontinue study intervention, without prejudice to further treatment. A participant who discontinues study intervention is normally expected to continue to participate in the study for the 30 day safety follow-up unless they specifically withdraw their consent to all further participation in any study procedures and assessments (see Section 7.2).
- Severe non-compliance with the CSP as judged by the investigator or AstraZeneca.
- Pregnancy or intent to become pregnant.
- Initiation of subsequent therapy for NF1-PN, including another investigational agent.
- Participants who experience disease progression based on the investigator's decision.

Note that discontinuation from study intervention is NOT the same thing as a withdrawal from the study.

Crossover within the study will be permitted (see Section [6.1.1](#) for details).

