### **7.1.1 Follow-up of Participants Post Discontinuation of Study Intervention**

All participants who discontinue the study intervention will be followed up for safety assessments 30 days after their last dose of study intervention. Additional assessments to be performed at the time of the 30 day safety follow-up are detailed in the SoA ([Table 1](#)).

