3.3.2 Study Periods

3.3.2.1 On-Treatment MRI Volumetric Assessments

On-treatment MRI volumetric assessments data will be defined as data after the date of first dose of study intervention until the study intervention discontinuation date or DCO, whichever occurs first. For analyses using the Extended Selumetinib FAS, volumetric assessments prior to the first dose of selumetinib will not be considered on-treatment MRI volumetric assessments.

Unscheduled scans will be considered for the on-treatment MRI volumetric assessments if those scans are not excluded due to prolonged study intervention interruption as described in Section 4.2.1.6.

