4.2.5.2 Derivations and Censoring Rules

Patients who have not progressed or died at the time of analysis will be censored at their last evaluable MRI assessment. However, if the patient progresses or dies after two or more consecutive missed MRI assessments, the patient will be censored at the time of the latest evaluable MRI assessment prior to the missed visits. The details of censoring rules are listed in Table 12.

The derivation formula for PFS is date of PFS event or censoring – date of randomisation + 1.

If the patient has no evaluable MRI assessments post-baseline, they will be censored at Day 1 unless they die within two cycles from baseline. The PFS time will be derived based on actual MRI assessment dates and not visit dates.

Table 12: Summary of Censoring Guidelines for PFS

Assessment	Date of event, death or censoring	PFS outcome
Death, PD	MRI assessment of earliest sign of PD or death date if the event is death	Event
No PD or death at time of analysis or lost to follow-up	Latest evaluable MRI assessment	Censored
Death or PD after ≥ 2 missed assessments	Latest evaluable MRI assessment prior to the two missed assessments	Censored
No evaluable MRI assessment or no baseline data and no death within two cycles from baseline	Day 1	Censored

MRI, magnetic resonance imaging; PD, progressive disease; PFS, progression-free survival.

Based on the scheduled visit assessment scheme (i.e., every 4 cycles until Cycle 24 and every 6 cycles from then onwards), the definition of 2 missed visits will change over time and is calculated as the protocolled time between 2 subsequent scans + the protocol-allowed visit window for an early visit at the previous assessment + the protocol-allowed visit window for a late visit at the expected assessment:

Table 13: Two Missed Visits Window Rule

Scheduled assessments	Previous REiNS assessment	Two missed visits window
Q16w ± 1 week up to Week 80	Up to Week 15 (<Day 105)	33 weeks (231 days)
	Week 15 – Week 79 ≥105 - <553	34 weeks (238 days)
	Week 79 – Week 95 ≥ 553 - <665	42 weeks (294 days)
Q24w ± 1 week	Week 95 ≥665	50 weeks (350 days)

REiNS, Response Evaluation in Neurofibromatosis and Schwannomatosis.

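### Stops for investigator-assessed progression that ICR has not called progressive disease are censored in PFS, TTP and DoR, and no planned analysis tests that censoring

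*Protocol*

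**What the plan says.** The protocol separates the person who decides on treatment from the body that decides on the endpoint. Section 8.1.1 states that "the management of participants will be based upon the results of the PN assessments conducted by the investigator using their standard of care methods". The list in 7.1 opens with "Participants may be discontinued from study intervention in the following situations", and one entry reads "Participants who experience disease progression based on the investigator's decision". ICR agreement is needed only for unblinding and early crossover in the randomised period (6.1.1, 8.1.1), and ICR reads are in general not passed back to sites.

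Scanning ends with treatment. Section 8.1.1 continues tumour assessments "as long as the participant remains on study intervention". Those words are attached to the schedule after Cycle 24, but the same follows for earlier stops: the MRI row of Table 1 has no entry at end of treatment or safety follow-up, and 7.1.1 provides only that "All participants who discontinue the study intervention will be followed up for safety assessments 30 days after their last dose of study intervention".

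In the SAP, the on-treatment scan window (3.3.2.1) runs "until the study intervention discontinuation date or DCO, whichever occurs first". Table 8 excludes later scans, and 4.2.4.3, 4.2.5.3 and 4.2.6.3 carry that to DoR, PFS and TTP. Events are ICR progression, plus death for PFS and DoR. For everyone else, 4.2.5.2 says: "Patients who have not progressed or died at the time of analysis will be censored at their last evaluable MRI assessment". Section 4.2.6.2 does the same for TTP, and 4.2.4.2 gives DoR the PFS censoring.

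**The concern.** Kaplan-Meier estimation assumes that a censored participant carries the same future risk as those still being scanned. A participant whose investigator has just judged the disease to be progressing is the one for whom that is least plausible.

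Discordance between the two judgements is foreseeable, because they rest on different definitions. REiNS progression needs a volume increase of at least 20% or a new PN (Protocol 8.1.1). The adverse-event guidance in Protocol 8.3.7 lets new or worsening NF1-PN symptoms count as progressive disease.

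The SAP already sees this elsewhere. Table 3 in 3.3.9 classes discontinuation before Cycle 12 for progressive disease as attributable, and 4.2.2.1.6 and 4.2.2.2.6 give such stops a missing-not-at-random sensitivity analysis for both key secondary endpoints. For PFS, TTP and DoR, where progression is itself the outcome, there is no counterpart. These are single-arm curves, so no control arm would show the effect.

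**Working it through.** **Tracing the rules for one participant.**

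1. The investigator judges progression by local methods and stops the drug. This is permitted by 7.1.
2. Every scan up to that date, scheduled or not, goes to ICR (8.1.1). If ICR calls progressive disease on any of them, the participant is an event.
3. If ICR does not, no further scan is scheduled, and any scan that is taken falls outside the window in SAP 3.3.2.1.
4. The participant is censored at the last evaluable MRI.
5. The supplementary analyses in SAP 4.2.4.5, 4.2.5.5 and 4.2.6.5 vary the interruption scans, the two-missed-assessment rule and the population, and add a listing. None alters step 4.

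**Size.** The documents state no event count, rate or assumed curve for these endpoints and no discordance rate between investigator and ICR, so there is no plan figure to reproduce. The rest is an illustration for PFS.

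Inputs from the documents: six scans to Cycle 24 (Cycles 4, 8, 12, 16, 20, 24) and 73 participants randomised to selumetinib. Assumed inputs:
- p = 2%, the probability of ICR progression per scan
- q = 0 to 2%, the probability per scan of a stop for progression that ICR does not call
- f, the share of those stops that would meet ICR progression at the next scan had scanning continued

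Formulas, with r = 1 − p − q:
- Planned estimate: (1 − p)^6 = 0.98^6 = 88.6%. It does not contain q.
- Every discordant stop counted as an event: r^6.
- ICR PFS with scanning continued: r^6 + q·r^5 + (1 − f)·q·Σ(j=1 to 5) r^(j−1)·(1 − p)^(5−j).
- Expected discordant stops: 73·q·(1 − r^6)/(p + q).

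Worked for q = 2%: r^6 = 0.96^6 = 78.3%, and the stops number 73 × 0.02 × (1 − 0.783)/0.04 = 7.9.

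| q per scan | Stops of 73 | Planned | Stops as events (gap) | Continued scans, f = 1 (gap) | Continued scans, f = 0.5 (gap) |
|---|---|---|---|---|---|
| 0 | 0 | 88.6% | 88.6% (0) | 88.6% (0) | 88.6% (0) |
| 0.5% | 2.1 | 88.6% | 85.9% (2.7) | 86.3% (2.3) | 87.5% (1.1) |
| 1% | 4.1 | 88.6% | 83.3% (5.3) | 84.2% (4.4) | 86.4% (2.2) |
| 2% | 7.9 | 88.6% | 78.3% (10.3) | 79.9% (8.7) | 84.3% (4.3) |

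With f = 0 the continued-scan figure is 88.6% to 88.8%, so there is no overstatement. The planned column is the same in every row: the planned curve cannot show whether discordant stops occurred.

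**The case against.** A reader might infer that everyone stopped for progression is counted as progression-free, and that durability is therefore overstated. The documents support neither step. A scan that prompts a stop will normally precede it, so it lies inside the window and is read by ICR; if it meets REiNS progression it is an event. ICR progression in participants who stay on drug counts too, and stopping is permitted rather than required. Only discordant stops are censored. Overstatement then needs those participants to have a raised risk of later ICR progression, and the documents give no rate for that.

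It is also fair that the estimand is deliberately ICR-read and on-treatment. A discordant stop is not, on the evidence to that date, an endpoint event. Counting all such stops as events measures something different and could err downwards, particularly where the stop was for symptoms.

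Nor is the plan silent. Disposition is tabulated by reason for stopping, with individual listings (SAP 4.1.1.2). Subject-level times are listed at the second and third data cut-offs, and swimmer plots are drawn for responders (4.2.4.4). A determined reader could count the affected participants.

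All of that stands as a limit on size and certainty. What it leaves is that no re-estimated curve is planned and nothing ties the count of such stops to the Kaplan-Meier estimates.

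**Conclusion.** The point holds for discordant stops only. Their censoring is potentially informative, with a likely optimistic direction, and no supplementary analysis tests it.

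Under an assumed 2% ICR progression per scan and 0 to 2% discordant stops per scan, 24-cycle PFS would be overstated by 0 to about 10 points. The upper end requires that every such stop be a true event. If half would meet ICR progression at the next scan, the gap is about 1 to 4 points for stop rates of 0.5 to 2%. If there are no such stops, or none would progress, it is zero. TTP and DoR share the mechanism, but no figure is offered for them.

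A reader might also infer that the trial's main conclusion is at risk. It is not: these are secondary, single-arm, descriptive summaries (Protocol 9.4.2.3.2 to 9.4.2.3.4) outside the multiple testing procedure, and neither the primary test nor its alpha depends on them. This is a cheap improvement to the durability evidence.

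**What to change.** Add one supplementary analysis to each of SAP 4.2.4.5, 4.2.5.5 and 4.2.6.5, with all other rules unchanged, in which two things also count as events:

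- discontinuation with progressive disease as the recorded reason and no earlier ICR progression, dated at discontinuation;
- ICR progression on any available scan after discontinuation and before subsequent NF1-PN therapy. Few are expected, since none is scheduled.

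Beside each Kaplan-Meier table, report the number censored after a stop for progressive disease. The ICR on-treatment analysis stays primary, and no visit, scan or treatment rule changes.

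The cost is SAP wording and one repeat run per endpoint; the reason for stopping is already collected. The downside is that the added events are not centrally read. The recorded reason, as listed in SAP Table 3, does not separate imaging from symptomatic progression, so some added events may not be REiNS progression. The result should be presented as a bound on the planned estimate and not as a replacement for it.

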### **8.1.2 Independent Central Review of Scans**

Independent central review of scans will be conducted as described in Section 8.1.1. A double read of all MRI scans will be performed. The ICR reviewers will be blinded to study intervention group.

### **8.1.3 Objective Response Rate**

Objective response rate is defined as the proportion of participants who have a confirmed CR (defined as disappearance of the target PN, confirmed by a consecutive scan within 3 to 6 months after the first response) or confirmed PR (defined as a target PN volume decrease  $\geq 20\%$ , compared to baseline, confirmed by a consecutive scan within 3 to 6 months after the first response) as determined by ICR per REiNS criteria.

### **8.1.4 Progression Free Survival**

Progression free survival is defined as the time from the date of first selumetinib dose until date of progression by ICR per REiNS criteria or death (due to any cause).

### **8.1.5 Duration of Response**

Duration of response will be defined as the time from the date of first documented response (which is subsequently confirmed) until date of documented progression by ICR per REiNS

criteria or death due to any cause.

